- a. Study design, including the sequence and timing of study procedures (distinguish research procedures from those that are part of routine care).

The study will be a randomized controlled trial of RP patients randomized to receive perioperative pharmacologic prophylaxis (subcutaneous heparin; 5,000 units given before surgery and every 8 hours after surgery until discharge) with IPCs or routine care with IPCs alone. No other standard post-RP practices will be affected. Per routine, all patients will be encouraged to ambulate early.

Routine care includes an initial clinic consultation, a preoperative evaluation center (PEC) visit prior to surgery (often done the day before surgery), and a planned 1 to 2 night inpatient stay after surgery. Patients currently receive IPCs but no pharmacologic prophylaxis in our default practice at Johns Hopkins. Patients are often given the option of returning to the Johns Hopkins clinic or local follow-up (with a provider or at home) for urinary catheter removal at around 10 days from surgery. Patients who were referred by outside urologists or providers may then decide if they wish to be followed at Johns Hopkins or locally for routine post-RP surveillance for cancer recurrence. Our current default practice at Johns Hopkins of no pharmacologic prophylaxis is considered inappropriate for most other major surgeries. However, both arms of this trial are considered routine standards of practice in the United States.

Informed consent will be obtained before surgery at either their urology or PEC clinical visit, or in the preoperative area the day of surgery. Eligibility will be confirmed at the time of consent. Patients will be randomized after consent is obtained and their surgery is officially scheduled to minimize dropout. Randomization will be done in blocks and stratified by whether patients choose to undergo an option 30-

day lower extremity Duplex ultrasound (outlined below) and whether they are having open or minimally-invasive (robotic/laparoscopic) surgery.

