1. Men 18-100 years of age with histologically confirmed prostate cancer of any stage undergoing RP
2. Normal preoperative coagulation blood test (prothrombin time)
3. Patients who would have otherwise been eligible to receive routine post-RP care

Exclusion:

1. Active treatment for VTE
2. Patients judged by their urologist or PEC center to be unsafe to forgo pharmacologic prophylaxis or systemic anticoagulation postoperatively (whether or not they are on systematic anticoagulation for indications other than VTE)
3. Known adverse reactions to heparin (heparin-induced thrombocytopenia or any allergy)
4. Epidural analgesia
5. Spinal anesthesia
6. Participation in a different trial that increases a patient's risk of VTE

6. Drugs/ Substances/ Devices

- a. The rationale for choosing the drug and dose or for choosing the device to be used.

Subcutaneous heparin and LMWH are routine agents for perioperative pharmacologic VTE prophylaxis. No randomized controlled trials have evaluated their use in the RP population to prevent VTE in the modern area of early ambulation and IPCs. A retrospective study reported that while LMWH reduced the rate of VTE, it could potentially increase the overall rate of bleeding/hematomas and lymphoceles compared to not receiving LMWH [29]. Subcutaneous heparin, however, does not appear to increase the rate of postoperative pelvic lymphoceles evaluated by screening ultrasound [25]. Additionally, subcutaneous heparin and LMWH were found to be equally effective at preventing VTE in a colorectal population [30]. Therefore, to minimize risk of complications and derive the greatest potential benefit, patients will receive standard prophylactic dosing of subcutaneous heparin at 5,000 units once before surgery (within 3 hours prior to incision) and then every 8 hours postoperatively.

- b. Justification and safety information if FDA approved drugs will be administered for non-FDA approved indications or if doses or routes of administration or participant populations are changed.

N/A – drugs are being used for approved indications.

- c. Justification and safety information if non-FDA approved drugs without an IND will be administered.

N/A – drugs are being used for approved indications.

7. Study Statistics

- a. Randomization scheme.

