Randomization by blocks will be used, with stratification for type of surgery (robotic/laparoscopic vs. open) and subcohort membership (agrees to 30 day ultrasound/does not agree to 30 day ultrasound). Currently at Johns Hopkins approximately 40% of RPs are performed open, with the remainder robotic or laparoscopic, and the subcohort is planned to include 200 patients. Note that patients are randomized within each of the 4 subgroups formed by cross classification of these 2 strata, not randomized to the strata. Therefore, anticipated sizes of the 4 strata are

1. open RP/subcohort member, n=80
2. open RP/not subcohort member, n=186
3. robotic RP/subcohort member, n=120
4. robotic RP/not subcohort member, n=280

Because the above numbers are subject to variability in the choice of surgical approach, randomization lists will increase the number in each of the surgical categories by 20%, i.e. 320 and 480 random assignments will be generated for open and robotic surgeries, respectively. An undisclosed block size will be used to prevent any ability to predict next treatment assignment. The randomization lists will be generated by [name] using SAS PROC PLAN. Although this uses a pseudorandom number generator it has the advantage of reproducibility when the same seed is used. [name] will maintain the randomization list, password protected, on a remote drive maintained by the Department of Urology, and will provide the random assignment to the study coordinator as each patient is enrolled. Because surgery dates are scheduled weeks in advance, there is no concern about inability to access the randomization list. A biostatistician who works for [name] and is not otherwise connected to this trial will also have access to the random assignments and can provide them to the study coordinator in the unlikely event that [name] is unavailable. Only [name] and the biostatistician ([name]) have access to the remote drive.

b. Primary outcome variable.

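### Eligibility is confirmed once, at consent, so a man who consents in clinic can be randomised before the PEC judgement that forms part of exclusion 2; late findings then act on one arm and dilute the comparison.

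*Combined protocol and SAP*

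**What the plan says.** Section 4a sets the sequence. On consent: "Informed consent will be obtained before surgery at either their urology or PEC clinical visit, or in the preoperative area the day of surgery". On eligibility and assignment: "Eligibility will be confirmed at the time of consent. Patients will be randomized after consent is obtained and their surgery is officially scheduled to minimize" (the stated aim is less dropout). The same section describes routine care as including "a preoperative evaluation center (PEC) visit prior to surgery (often done the day before surgery").

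Section 5 makes the PEC one of two possible judges of exclusion 2: "Patients judged by their urologist or PEC center to be unsafe to forgo pharmacologic prophylaxis" or systemic anticoagulation after surgery. It also requires "Normal preoperative coagulation blood test (prothrombin time") and excludes epidural analgesia and spinal anesthesia. It does not say when the blood test is taken, or when and by whom the anaesthetic plan is settled.

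Section 7a sends each assignment to the study coordinator at enrolment and adds: "Because surgery dates are scheduled weeks in advance, there is no concern about inability to access the randomization list".

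Section 4c blinds urologists to assignment until after surgery and does not mention patients, PEC staff or anaesthesia staff. Section 4f gives one ground for removal, surgery cancelled or not completed, and keeps all assigned patients who complete surgery in the ITT analysis whatever their dose compliance. Section 7d bases treatment success on ITT. No section describes a second eligibility check or says what happens when a patient is found ineligible after assignment.

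**The concern.** An eligibility criterion applied before randomisation removes patients from both arms alike. Applied afterwards, it need not. Exclusion 2 shows this most clearly: a man judged unsafe to go without prophylaxis or anticoagulation is in conflict with an assignment to compression devices alone, but not with an assignment to heparin. The other criteria lean the opposite way. An abnormal prothrombin time or a plan for epidural or spinal anaesthesia bears mainly on a man assigned to heparin.

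Two things are at stake. The first is the size of the treatment contrast. Controls who receive heparin, or heparin patients who do not, pull the two event rates together, and the design has little power to spare (80% required, 82% by simulation). The second is consistency. With no written rule, staff must improvise for each late-ineligible patient, and the ITT set is then only as sound as those decisions.

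**Working it through.** **1. Sequence.** For a man who consents at the urology visit, the plan permits this order: consent, eligibility confirmed, surgery scheduled, randomised (Section 4a), with surgery weeks ahead (Section 7a); then the PEC visit, often the day before surgery; then surgery. One of the two judgements named in exclusion 2 can therefore follow assignment. The problem does not arise for a man who consents on the day of surgery, or at the PEC once its assessment is complete.

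**2. The plan's own power figure.** Inputs from Sections 7d and 7e: control rate 5%, heparin rate 1.5%, 333 per arm, one-sided alpha 0.05. The normal approximation for two proportions is

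power = Φ[(pC − pH − 1.645·SE0)/SE1], with SE0 = √[2·p̄(1 − p̄)/n] and SE1 = √{[pC(1 − pC) + pH(1 − pH)]/n}.

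Here p̄ = 0.0325, SE0 = 0.01374 and SE1 = 0.01368. The argument is (0.035 − 1.645 × 0.01374)/0.01368 = 0.906, giving 81.8%. A three-look simulation with nominal cut-offs .001, .015 and .048 and the stated interim futility limits gives 82.5%. Both agree with the stated 82%. The rest uses the fixed-sample formula.

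**3. Crossover under ITT.** Assumptions not in the documents: a share f of controls is found unsafe to forgo prophylaxis after assignment and receives heparin, and their untreated risk is r. The risk reduction is taken as 70%, which is the plan's own 5% to 1.5%. The overall untreated control rate is held at 5%. Then

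pC = (0.05 − f·r) + 0.3·f·r = 0.05 − 0.7·f·r.

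The heparin arm stays at 1.5%.

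| f | r | pC | Power |
|---|---|---|---|
| 0 | – | 5.00% | 81.8% |
| 1% | 5% | 4.97% | 81.3% |
| 1% | 15% | 4.90% | 80.2% |
| 3% | 5% | 4.90% | 80.2% |
| 3% | 15% | 4.69% | 76.8% |
| 5% | 5% | 4.83% | 79.1% |
| 5% | 10% | 4.65% | 76.2% |
| 5% | 15% | 4.48% | 73.0% |

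Of 333 controls, 1% to 5% is about 3 to 17 men. In the worst row, expected control events fall from 16.7 (0.05 × 333) to 14.9 (0.04475 × 333).

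**4. Sensitivity to the meaning of the 5%.** Suppose 5% is instead the rate among men who pass exclusion 2. With f = 5% and r = 15%, the late-found men carry a treated risk of 0.3 × 0.15 = 4.5% in both arms. Then pC = 0.95 × 0.05 + 0.05 × 0.045 = 4.975%, pH = 0.95 × 0.015 + 0.05 × 0.045 = 1.65%, and power is 77.5%, inside the range above.

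**5. The heparin side.** If a share y of the heparin arm goes without heparin at average risk, pH = (1 − y)·0.015 + y·0.05. For y = 2%, pH is 1.57% and power 80.0%. For y = 5%, pH is 1.675% and power 77.2%. This depends on prothrombin time or anaesthetic plan being settled late, which the documents do not state.

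**The case against.** The best reply is that the plan already governs these patients. Section 4f keeps everyone who completes surgery in the analysis, and Section 7d rests treatment success on ITT. That stands, and it decides the form of the harm. A reader might infer that high-risk controls would be dropped, biasing the contrast. For example, dropping 5% of controls with a 10% risk would leave (0.05 − 0.005)/0.95 = 4.74%, a shift against heparin. The plan provides for no such removal, so selective loss would arise only if staff departed from it.

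A reader might also infer that the PEC settles several criteria, or that those making late judgements know the arm. Neither is documented. Section 5 names the PEC for one criterion, jointly with the urologist, who could make that judgement at a clinic visit. Urologists are blinded before surgery, and the plan says nothing about what PEC or anaesthesia staff know. Arm-influenced judgement is possible but not shown. Crossover does not need it: a late finding conflicts with only one assignment, however it was reached.

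Finally, consent and scheduling fix only the earliest point for randomisation, and the remark about weeks in Section 7a concerns access to the list. Sites could wait in doubtful cases. This also stands, so the frequency is unknown. But nothing in the text requires waiting, and nothing calls for a second check.

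**Conclusion.** The concern holds as a gap in sequencing and in rules. The plan allows assignment before one named exclusion criterion can be fully assessed, describes no re-check, and does not say how ineligibility found after assignment is handled. The expected consequence is control-arm crossover and dilution of the primary comparison. Biased selection is not supported by the documents.

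The size cannot be established from the documents. On the assumed ranges, power falls from 81.8% to between 73.0% and 81.3%. At a 1% share it stays above the 80% target throughout; at a 5% share it is below it throughout, at 73.0% to 79.1%. The lowest value needs both the highest share and the highest risk. The figures also assume that a control found unsafe to forgo prophylaxis does receive heparin, which the plan does not state. How such a patient should be managed is a clinical matter on which this review takes no position. The change is worth making because it is cheap and leaves sample size, alpha and endpoints untouched.

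**What to change.** In Section 4a, keep consent at any of the three settings. Replace the single check at consent with a re-confirmation of eligibility, and release the assignment only once the prothrombin time result, the urologist or PEC judgement under exclusion 2 and the planned anaesthesia have been recorded.

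In Sections 4f and 7d, state that any patient found ineligible after assignment who completes surgery stays in the ITT analysis, and that such patients are reported by arm with the reason. State in Section 4c who may know the assignment before surgery.

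Reconcile the reassurance in Section 7a about list access with day-of-surgery consent in Section 4a. A backup list holder is already named there, so the means of prompt release (list holder, electronic module or sealed envelopes) can be left to the sponsor.

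The cost is protocol wording and arrangements for prompt release. The downside is that assignments are issued close to surgery, so the preoperative order is placed at short notice. Later release also fits the plan's own aim of limiting dropout, since fewer cancellations would follow randomisation.

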Patients randomized to the pharmacologic VTE prophylaxis arm will receive a dose of subcutaneous heparin 5,000 units within 2 hours prior to incision, and subcutaneous heparin 5,000 units every 8 hours after surgery until discharge. Total number of doses received and missed doses will be recorded. No post-discharge pharmacologic prophylaxis will be prescribed. Per routine care, patients will be requested to inform their urologist's office if they experience any symptoms of DVT or PE, or any other concerns, during the first 30 days after surgery. All patients will receive a phone call around 30 days after surgery to assess primary outcomes including documentation of whether they experienced a postoperative VTE episode and any treatment initiated for confirmed VTE. Any patient endorsing symptoms concerning for VTE up to 30 days after surgery will be recommended to undergo urgent evaluation and care, locally or at Johns Hopkins, with imaging/evaluation results forwarded to Johns Hopkins. Patients and their insurance will be responsible for the costs as part of routine care. The 30-day phone call will be the only planned, study-initiated contact after surgery with the patient to evaluate symptomatic outcomes and will be the same for both the control and pharmacologic prophylaxis arms.

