An optional part of the study protocol, a subcohort of at least 200 patients (funds allowing) will be offered a routine 30-day post-RP screening lower extremity Duplex ultrasound to assess for DVT at Johns Hopkins for patients willing to travel to Johns Hopkins to obtain the ultrasound in this time frame. Patients are not required to obtain this screening ultrasound, but initial randomization will be stratified by whether patients opt to undergo ultrasound (and robotic vs. open surgery) to ensure study arms are balanced. In other words, patients willing to undergo ultrasound will be identified before randomization. All patients, regardless of whether they undergo ultrasound, will be assessed for all primary outcomes as described. For the subset of patients who obtain the ultrasound, it will be used to assess the secondary outcome of any VTE (asymptomatic or symptomatic). The outcome of any VTE will be tabulated based on the results of the screening ultrasound and any report of a symptomatic VTE episode (assessed by call at 30 days as described above). Stratified randomization is outlined in Figure 1. Written informed consent includes a plan to inform the patient and their primary physician of the results of the ultrasound and any incidental findings. Costs for the screening ultrasound obtained as part of the study will be covered by the study. Symptoms prompting a recommendation for evaluation to rule out DVT or PE (appropriate diagnostics/imaging to be determined by evaluating physician) will include:

1. Persistent unilateral or bilateral lower extremity edema
2. Persistent calf pain or cramping
3. Persistent or new chest pain
4. Persistent or new shortness of breath that started suddenly or worsens with exertion
5. Productive cough with bloody sputum
6. Fever and/or tachycardia without any known source of infection
7. Any other clinical concern for DVT or PE

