The primary efficacy outcome will be the incidence of symptomatic VTE. The primary safety outcomes will include three separate measures of incidence of symptomatic lymphocele, incidence of symptomatic hematoma, or major bleeding within 30 days after surgery. The secondary outcomes (all regarded separately) will be estimated blood loss from surgery, total surgical drain output after surgery (for patients with surgical drains), the overall incidence of VTE (asymptomatic or symptomatic) determined from the subcohort undergoing lower extremity Duplex screening ultrasound, and surveillance bias (measured by use of postoperative diagnostic imaging, either as inpatient or within 30 days from surgery). Two planned interim analyses will be conducted as outlined in the study statistics section with early stopping rules due to adverse events or demonstrated futility.

[figure not shown]

Figure 1. Diagram of plan for stratified randomization of patients to arms and outcomes assessed.

b. Study duration and number of study visits required of research participants.

The study protocol will be largely implemented during routine visits required of all RP patients (described above) with the addition of a visit specifically for screening lower extremity Duplex for eligible patients as part of the run-in described above. Patients will be contacted by phone around 30 days after surgery to tabulate the primary and secondary outcomes. Patients may initiate contact before this point if they wish to report concerns or diagnosis of VTE. Any events that occur after 30 days and are reported by patients in an unsolicited fashion will be documented, but they will not be included as part of the primary outcome. There will be no planned contact initiated by the study team with patients after 30 days except to confirm documentation of VTE events that occurred up to 30 days from surgery due to symptoms or discovered on screening lower extremity Duplex ultrasound. Patients reporting symptoms concerning for VTE at or before the 30 day mark who are diagnosed within 2 weeks of reporting symptoms (even if after the 30 day mark) will be included as symptomatic VTE events for the primary outcome.

c. Blinding, including justification for blinding or not blinding the trial, if applicable.

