Urologists will initially be blinded to patient randomization and the administration of the preoperative subcutaneous heparin dose to prevent bias on recorded estimated blood loss during the surgery. Postoperatively, administration of subcutaneous heparin will be unblinded during the patient's inpatient stay. Control patients will receive IPCs only and no placebo doses will be administered during their hospital stay. Data analysis will be blinded as to treatment group. Performance and interpretation of lower extremity Duplex screening ultrasound will be blinded to patient randomization. Surveillance bias will be assessed by differential performance of postoperative imaging as described above.

- d. Justification of why participants will not receive routine care or will have current therapy stopped.

All patients will receive routine care. Both arms include patients receiving accepted standards of care.

- e. Justification for inclusion of a placebo or non-treatment group.

The control group in this trial is the group receiving current routine practice at Johns Hopkins with IPCs. The experimental group is the group receiving pharmacologic VTE prophylaxis as practiced at other centers and recommended by most VTE guidelines for major surgery.

- f. Definition of treatment failure or participant removal criteria.

Participants will be removed from the trial if surgery is canceled or not completed for any reason. All patients assigned to the experimental and control arms completing surgery will be included in the study regardless of compliance with pharmacologic prophylaxis doses in an intention-to-treat (ITT) analysis. Patients experiencing an adverse event will be provided appropriate care. Additional per-protocol analyses will be conducted to compare outcomes by compliance with assigned regimen. Patients diagnosed with VTE events will be recommended to obtain routine care locally or at Johns Hopkins per patient preference.

- g. Description of what happens to participants receiving therapy when study ends or if a participant's participation in the study ends prematurely.

Perioperative pharmacologic prophylaxis is only given during the patient's inpatient stay. As mentioned above, all patients will be included in an ITT analysis as possible if they undergo surgery. No planned outcomes will be tracked after the 30-day post-surgical outcomes unless the patient initiates contact.

5. Inclusion/Exclusion Criteria

Inclusion:

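### The plan does not say who makes the day-30 call or whether that person is masked to arm, although the call can create primary events; a masked caller or a fixed script would be a cheap improvement.

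*Combined protocol and SAP*

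**What the plan says.** Section 4a (study design) gives the call its role: "All patients will receive a phone call around 30 days after surgery to assess primary outcomes". It adds that no other study-initiated contact after surgery is planned to evaluate symptomatic outcomes, and that the call "will be the same for both the control and pharmacologic prophylaxis arms". On what follows: "Any patient endorsing symptoms concerning for VTE up to 30 days after surgery will be recommended to undergo urgent evaluation and care".

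The symptom list in 4a, repeated in 7b (primary outcome), has seven items. Several turn on whether a symptom is persistent, and the last is "Any other clinical concern for DVT or PE". The type of work-up is left open: "appropriate diagnostics/imaging to be determined by evaluating physician".

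Section 4b extends the counting window: "Patients reporting symptoms concerning for VTE at or before the 30 day mark who are diagnosed within 2 weeks of reporting symptoms" are primary events even when the diagnosis falls after day 30. Section 7b requires imaging confirmation after a symptom-prompted evaluation, except for deaths attributed to VTE on clinical suspicion without autopsy.

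Section 4c (blinding) masks the urologist at first, so that recorded blood loss is not influenced, and it masks the data analysis. It also says: "Performance and interpretation of lower extremity Duplex screening ultrasound will be blinded to patient randomization". After surgery heparin is given openly, with no placebo for controls. The caller is not mentioned. Section 7a says the holder of the randomization list "will provide the random assignment to the study coordinator as each patient is enrolled".

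**The concern.** A symptomatic VTE becomes a primary event only if someone hears of the symptom and it is worked up. For events not already diagnosed by day 30, that step runs through the call. A caller who knows the arm may probe harder, or treat a vague complaint as more worrying, in one arm than in the other. Making the call the same in both arms fixes its intended content. It does not limit what the caller knows, and the plan contains no script.

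The masking in 4c does not reach this step. The masked scan is the screening Duplex, which serves the secondary any-VTE outcome in the subcohort. No masking is stated for the diagnostic work-up behind the primary outcome.

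Events will be few, so a small difference in detection matters. The plan's secondary outcome on imaging use by arm may reveal unequal work-up, but it neither prevents it nor corrects the primary comparison. Nor can it separate unequal questioning from a true difference in symptoms.

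**Working it through.** **Inputs from the plan.** 333 patients per arm; 5% versus 1.5% symptomatic VTE; one-sided α 0.05 (7d). Looks at 222, 444 and 666 patients, that is 111, 222 and 333 per arm; O'Brien-Fleming efficacy boundaries; interim futility bounds p = 0.816 and 0.272 (7e).

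**Inputs assumed.** The plan prints alpha spent, not z values, so I used O'Brien-Fleming boundaries of 2.96, 2.09 and 1.71. The share of heparin-arm events lost, q, is not in the documents and is varied.

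**Step 1. The plan's own figure.** The test at each look is z = (p_C − p_H) / √[2p̄(1 − p̄)/n], with n per arm and p̄ the mean of the two rates. Exact binomial enumeration over the three looks at 5% versus 1.5% gives 82.5% power, against the stated 82%. The model reproduces the design.

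**Step 2. How few events decide the result.** Expected events are 333 × 0.05 = 16.7 in controls and 333 × 0.015 = 5.0 on heparin. At 333 per arm:

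- 17 versus 8: difference 9/333 = 0.0270, p̄ = 25/666 = 0.0375, z = 1.83, one-sided p = 0.033.
- 17 versus 9: difference 8/333 = 0.0240, p̄ = 26/666 = 0.0390, z = 1.60, one-sided p = 0.055.

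One event more or less in the heparin arm moves the result across the final boundary of 1.71.

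**Step 3. Error rate under assumed unequal capture.** With no true effect, set the control rate to p and the detected heparin rate to p(1 − q), then run the same enumeration. The two base rates are 3.25%, the mean of 5% and 1.5%, and 5%.

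| q: share of all heparin-arm events lost (assumed) | True VTE 3.25% | True VTE 5% |
|---|---|---|
| 0 | 5.0% | 4.9% |
| 2.5% | 5.6% | 5.6% |
| 5% | 6.3% | 6.5% |
| 10% | 7.9% | 8.6% |
| 20% | 12.2% | 14.5% |

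**Step 4. What part of this the call could cause.** q applies to all heparin-arm events, but the caller affects only those not yet diagnosed. If a quarter of events first surface at the call (assumption) and 10% to 20% of those are lost, then q = 0.25 × 0.10 = 2.5% to 0.25 × 0.20 = 5%. The 2.5% and 5% rows show this case. The 10% and 20% rows would need losses across all symptom-triggered ascertainment.

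**Step 5. The other direction.** Under the planned 5% versus 1.5%, capturing only 80% of control events (a detected rate of 4%) lowers power from about 82% to 63%.

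**The case against.** The strongest reply is that the call is mostly a record of what has already happened. Patients are asked to report symptoms to the urologist's office throughout the 30 days, and the call documents episodes already diagnosed. In the screening series described in section 3, the seven patients who presented with symptoms after a negative scan did so within two weeks of surgery. This stands, and it is why the 10% and 20% rows are an upper range.

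Other safeguards also stand. The symptom list is fixed in advance, any patient endorsing symptoms is already to be advised to seek evaluation, and the evaluating physician rather than the caller chooses the imaging. Non-fatal events need imaging confirmation, and imaging use by arm is a named outcome. These narrow the caller's influence without removing it. Imaging confirmation limits false events but not unequal referral, and the open-ended last item leaves room for judgement.

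Two stronger readings are tempting. A reader might infer that the call is unmasked and made by the coordinator. The documents are silent on both; 7a says only that the coordinator receives assignments. A reader might also take 4c to mean that imaging for the primary outcome is masked, leaving the call as the only gap. Section 4c covers only the screening Duplex and states nothing on the physicians working up symptoms, the readers of diagnostic scans or whoever attributes deaths.

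**Conclusion.** The gap is real and modest: a cheap improvement. The plan leaves the caller's identity and knowledge of arm unstated, in a trial that is open after surgery, for the one planned contact that collects symptomatic outcomes and can generate primary events. Following the plan as written would permit unequal elicitation.

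The size and direction cannot be determined from the documents. With no true effect and losses confined to the heparin arm, the one-sided error goes from about 5% to 5.6%–6.5% for an assumed 2.5% to 5% loss of all heparin-arm events, and to 7.9%–14.5% for 10% to 20%. Both ranges cover true rates of 3.25% and 5%. A reader might take the upper range as the expected effect of an unmasked call, or conclude that the bias must favour heparin. Neither is supported: the upper range ignores events diagnosed before the call, and under-capture in controls would cost power instead.

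**What to change.** In 4a and 4c, state that the day-30 call is made by an existing team member without access to assignments, where one is available. Section 8c refers to one or more research coordinators, which does not establish that a second, unaware person exists, so the script below should apply whoever calls.

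- Ask the symptoms on the existing list that a patient can report, verbatim and in fixed order, as yes/no.
- For the call only, replace the last item, which is a clinician's judgement, with one fixed open question.
- Record the answers before opening the chart.
- Apply the evaluation recommendation already in 4a identically in both arms.
- Ask patients at the start not to mention injections.

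The cost is a short script and a task assignment. Treatment, sample size and analysis are unchanged. Masking will be imperfect because patients know whether they had injections, and for the same reason any extra referrals need not be equal between arms. The script does not mask the later work-up or the attribution of deaths.
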